### **4.4.2 Secondary efficacy analyses**

Secondary efficacy endpoints will be presented for PP.

## **SAB-HLA**

SAB-HLA levels (MFI) are determined at pre-dose and 2, 6, 24 and 48 hours and days 7, 14, 21, 28, 64, 90, 120 and 180 days post imlifidase treatment. Positive SAB-HLA are defined as having pre-dose levels above 3,000 MFI. The SAB-HLA will be listed by patient flagging positive (yes/no) and donor specific SAB-HLAs. The positive SAB-HLA will be summarised and presented in box-plots.

## **DSA**

DSA levels (MFI) are determined at pre-dose and 2, 6, 24 and 48 hours and days 7, 14, 21, 28, 64, 90, 120 and 180 post imlifidase treatment. The DSA will be summarised by patient and time point. DSA will be presented graphically as scatter plots (MFI versus time) with one separate plot for each patient. The x-axis in these plots will be with the nominal time points and therefore not linear in the time variable. For this reason the scatter plots will be without connecting lines.

## **Pharmacodynamics**

The PD profile of imlifidase (cleavage and recovery of IgG) is recorded up to day 180 post imlifidase dosing. PD will be summary tabulated by time point and presented graphically as mean profile versus time and as spaghetti profile plots.

All PD data will be presented for the PP analysis set.

## **Time to negative crossmatch**

The time to creating a negative crossmatch is specified in the protocol as an endpoint. However, due to many missing values and in particular missing data for time points between pre-dose and 24 hours, the Time to creating a negative cross match will not be calculated. Crossmatch data will be listed.

## **Pharmacokinetics**

The PK profile of imlifidase is recorded up to day 14. The PK concentrations will be summary tabulated by time point. The PK summary tables will not include total columns. Further, the PK concentrations will be presented graphically as mean profile plots by number of doses and as spaghetti plots. Semi-log format with log10 y-axis and a linear time x-axis will be presented.

The PK parameters are derived as described above under pre-processing by compartment modelling. Further NCA parameters are calculated from the compartment parameters. Both types of PK parameters will be summary tabulated. In addition to standard summary measures,  $t_{1/2}$  will be described by the harmonic mean.

Imlifidase values <LLOQ (LLOQ = 0.10 µg/mL) will be presented as 0.5\*LLOQ for summary tables and figures.

All PK data will be presented for the PP analysis set.

### **4.4.3 Additional analyses**

Calculated PRA (cPRA) values will be summarised using the undiluted categories <80%, 80.00% - 97.50%, 98% (97.51% - 98.50%), 99% (98.51% - 99.50%), > 99% (99.51% - 100%).

Additionally, the diluted and undiluted cPRA values will be plotted against the different cut-off for unacceptable HLA.

## 4.5 Safety

Safety parameters will be evaluated for the safety analysis data set.

### 4.5.1 Adverse events

Adverse events (AEs) will be classified according to the Medical Dictionary for Regulatory Activities (MedDRA) version 18.1.

A treatment emergent adverse event (TEAE) is any AE occurring after the administration of the IMP and within the time of the residual effect period or a pre-treatment AE or pre-existing medical condition that worsens in intensity after administration of the IMP and within the time of the follow up period. Based on the half-life and the PD properties of imlifidase the residual drug effect is considered 30 days after administration.

An AE overview summary table will be prepared including the number of patients reporting an AE, the percentage of patients (%) with an AE, and the number of events (E) reported for the following categories:

- TEAEs
- Related TEAEs
- Serious TEAEs (SAEs)
- TEAEs leading to withdrawal
- Deaths

Treatment-emergent AEs will be summarised in a table by dictionary level, i.e., SOC and PT for MedDRA. The table will display the total number of patients reporting an AE, the percentage of patients (%) with an AE and the number of events (E) reported. AEs will be presented by SOC and PT sorted in decreasing frequency of occurrence.

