A follow-up visit will be performed 180 +/- 14 days following IdeS infusion. This will be considered the end of study for the patient. At this visit the patient will be assessed for vital signs, ECG, AEs and concomitant medication. Blood sampling for analysis of DSAs, pregnancy test, safety laboratory tests, P-creatinine/eGFR, PD and ADA will be performed and e GFR calculated. Urine will be obtained for assessment of proteinuria and a physical examination will be performed. A kidney biopsy will be performed to assess kidney status.

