6.3.1 Definition of adverse events

An adverse event (AE) is the development of an undesirable medical condition or the deterioration of a pre-existing medical condition following or during exposure to a pharmaceutical product, whether or not considered causally related to the product. Relationship to the study drug will be deemed as not related, unlikely, possible or probable. An undesirable medical condition can be symptoms (e.g. nausea and chest pain), signs (e.g. tachycardia and enlarged liver) or the abnormal results of an investigation (e.g. laboratory findings and electrocardiograms).

In cases of surgical or diagnostic procedures, the condition/illness leading to such a procedure is considered as the AE rather than the procedure itself.

In case of fatality, the cause of death is considered as the AE, and the death is considered as its outcome.

Pre-treatment adverse event:

A pre-treatment adverse event is any untoward medical occurrence arising or observed between signing of informed consent and the first administration of the IMP.

Treatment emergent adverse event:

A treatment emergent adverse event is any AE occurring after the administration of the IMP and within the time of the follow up period or a pre-treatment adverse event or pre-existing medical condition that worsens in intensity after administration of the IMP and within the time of the follow up period.

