6.3.3 Recording of adverse events

In clinical studies, an AE/SAE can occur at any time after signing of the informed consent until the end of the study, including run-in or washout periods, even if no study treatment has been administered, e.g. and AE can be related to a procedure in the protocol.

AEs will therefore be collected on the AE CRF from the time of signing of the informed consent and throughout the study period including the follow-up period. However, AEs that occur in the time period between informed consent and administration of the trial drug should be recorded as part of the patient's medical history, but will not be considered a treatment emergent adverse event (TEAE) unless directly related to study procedures (e.g. hematoma secondary to laboratory testing) or it meets the definition of an SAE.

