12.2.3 Safety and tolerability

All safety and tolerability data will be listed as specified in the SAP.

Adverse events will be collected for each patient from visit 1 until follow-up. Serious adverse events will be recorded from the time when informed consent is obtained (Visit 1) until the follow-up visit.

The following summaries of AEs will be given by treatment and in total:

The number of patients who had any AEs, SAEs, AEs that led to withdrawal, AEs related to study drug and AEs with severe intensity.

If the number of AEs is sufficiently large, summaries will be presented by PT (Preferred term) and SOC (System organ class) according to MedDRA vocabulary.

Severity, time of onset, duration, action taken, concomitant therapy started and patient outcome of the AEs will be given in data listings only. AEs which were reason for premature discontinuation of study drug will be listed separately.

Furthermore, SAEs and AEs that led to withdrawal will be listed separately.

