**The secondary objectives of this study are:**

- To determine DSA levels at multiple times (pre-dose, 2, 6, 24 and 48 hours and days 7, 14, 21, 28, 64, 90, 120 and 180) post imlifidase treatment
- To determine time to creating a negative CDC crossmatch test
- To determine time to creating a negative FACS crossmatch test
- To evaluate safety parameters (adverse events, clinical laboratory tests, vital signs and ECGs) following imlifidase treatment up to day 180
- To monitor kidney function after imlifidase treatment as assessed by, filtration (eGFR), creatinine and proteinuria
- To establish the PK profile of imlifidase
- To establish the PD profile of imlifidase (cleavage and recovery of IgG)
- To establish the immunogenicity profile of imlifidase (ADA)

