## 4 Statistical analyses and presentation of data

### 4.1 General considerations

No formal statistical hypothesis testing will be performed in this study. All presentation of data will be descriptive by nature. Missing data will in general not be imputed or adjusted for in other ways.

The protocol states that tabulations will be by actual dose received. The protocol allowed for the DSMB to decide on dose escalation. All patients were administered planned dose(s) of 0.25 mg/kg BW. For one patient the actual dose was reduced due to an allergic reaction. For 3 patients the protocol option of administering a 2nd dose was used. Efficacy and safety tabulations will be by number of administrations (1 or 2 doses) and total including all patients. The patient with reduced dose [REDACTED] will be included in the “1 dose” group for safety evaluation but excluded from the PP.

Numerical data will be presented in summary tables by number of patients, arithmetic mean (geometric mean and coefficient of variation [CV] where applicable), median, standard deviation (SD), minimum and maximum. Categorical data will be presented by number and percent of patients as well as number of events (where applicable).

Endpoints will be presented graphically as mean profile plots, individual profile plots and spaghetti plots. The sampling frequency is for efficacy and some safety endpoints high from pre-dose until 48 hours followed by decreasing frequency. Therefore, the graphical presentation will, in most cases, be as box plots with a categorical x-axis. For other data, a plot with linear x-axis (0 to 180 days) may be supplemented with a subset plot where only the first 24 or 48 hours are included on the x-axis.

All data will be listed. Auxiliary database parameters will not be included. Listings will be sorted by patient ID, parameter and time point. In general listings will not be mentioned in detail below.

The study did not include any interim analyses.

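### The SAP counts new adverse events as treatment-emergent for 30 days only, where the protocol counts them to day 180, and does not declare the change

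*SAP*

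**What the plan says.** Protocol 6.3.1 gives the definition: "A treatment emergent adverse event is any AE occurring after the administration of the IMP and within the time of the follow up period". It applies the same follow-up limit to a pre-treatment event or existing condition that worsens. For the end of follow-up, the Visit 12 text in Protocol 6.2 says "A follow-up visit will be performed 180 +/- 14 days following IdeS infusion" and calls this the end of study for the patient. Protocol 6.3.3 collects AEs "throughout the study period including the follow-up period". Protocol 12.2.3 promises, with no 30-day limit: "The number of patients who had any AEs, SAEs, AEs that led to withdrawal, AEs related to study drug and AEs with severe intensity".

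SAP 1.1.1 keeps the safety objective: "To evaluate safety parameters (adverse events, clinical laboratory tests, vital signs and ECGs) following imlifidase treatment up to day 180". SAP 4.5.1 then repeats the protocol's definition but replaces the follow-up period with a residual-effect period for new AEs, and sets its length: "Based on the half-life and the PD properties of imlifidase the residual drug effect is considered 30 days after administration". The second half of the definition is unchanged and still covers a "pre-existing medical condition that worsens in intensity after administration of the IMP and within the time of the follow up period".

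SAP Section 5 lists one deviation from the protocol analysis, namely who performs the pharmacokinetic analysis. SAP 4.1 sets the columns of the tables: "Efficacy and safety tabulations will be by number of administrations (1 or 2 doses) and total including all patients".

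**The concern.** The two halves of the SAP definition run over different periods. A reason based on half-life and pharmacodynamics cannot support 30 days for a new event and about 180 days for a worsening. Followed exactly, the SAP produces a mixed count that matches neither the protocol's definition nor a consistent residual-effect definition.

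This is a single-arm, descriptive study, so AE incidence is itself the main AE result. A reader of the protocol would take the tabulated incidence to cover 180 days. For new non-serious events it would cover about the first month.

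Two further points are left open. The overview table has a row that equates SAEs with serious TEAEs, while the two SAE summary tables and the deaths row carry no such label; two programmers could apply different windows to these outputs. The SAP also does not say whether the 30 days start at the first or the last dose, although SAP 4.1 reports that 3 patients had two doses.

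**Working it through.** Neither document gives a figure to reproduce, so the check compares the texts and sizes the gap.

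**1. The definitions side by side**

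| | Protocol 6.3.1 | SAP 4.5.1 |
|---|---|---|
| New AE after dosing | follow-up period | 30 days |
| Worsening after dosing | follow-up period | follow-up period |
| New AE on day 60 | treatment-emergent | not treatment-emergent |
| Worsening on day 60 | treatment-emergent | treatment-emergent |

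**2. Where a new AE after day 30 would appear (SAP 4.5.1)**

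- Summary tables: 4 of 6 are labelled TEAE (all, by causality, by intensity, related by intensity). The event is in none of them.
- Overview rows: 4 of 5 are labelled TEAE. The fifth is deaths.
- The 2 SAE tables and the deaths row have no TEAE label, so their window is not fixed by the text.
- A non-serious event appears only in listings, chiefly the one for post-treatment AEs.

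**3. Share of follow-up outside the window for new AEs**

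Inputs: 30 days (SAP 4.5.1); final visit at day 180 ± 14, so day 166 to 194 (Protocol 6.2); second dose within 2 days of the first (SAP Section 2), so the window may end on day 32.

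Share = (follow-up − window) / follow-up

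- Nominal: (180 − 30)/180 = 150/180 = 83.3%
- Lowest: (166 − 32)/166 = 134/166 = 80.7%
- Highest: (194 − 30)/194 = 164/194 = 84.5%

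**4. Visits**

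The flow chart records AEs at visits 2 to 12, which is 11 visits. Days 64, 90, 120 and 180 fall after the cut: 4/11 = 36%. This is not a share of events; the day 64 visit will also pick up some events that began before day 30.

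**5. Share of events (assumption only)**

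The documents give no onset rates, so two sets of patterns were tried.

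*Step pattern.* The daily rate of new AEs after day 30 is r times the rate before. Share lost = 150r / (30 + 150r).

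- r = 0.1: 15/45 = 33%
- r = 0.25: 37.5/67.5 = 56%
- r = 0.5: 75/105 = 71%
- r = 1: 150/180 = 83%

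*Decay pattern.* The onset rate halves every h days, with k = ln 2 / h. Share lost = (e^(−30k) − e^(−180k)) / (1 − e^(−180k)).

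- h = 14: 23%
- h = 30: 49%
- h = 60: 67%
- h = 90: 73%

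These are illustrations and not bounds. A faster decay would give less than 23%.

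**The case against.** The strongest reply is that a residual-effect window is a recognised choice for a drug given once or twice. Later events mix with surgery, IVIg, rituximab and immunosuppression. The SAP states the 30 days openly with a reason, the protocol leaves analysis detail to the SAP, and Protocol 12.2.3 does not tie its promised counts to the TEAE label. No data are lost: everything is listed, there is a listing of post-treatment AEs, and laboratory, vital-sign, anti-drug-antibody and kidney-function summaries are not affected. With 15 to 20 patients, late events could be counted by hand. The table shells are separate documents and may settle the SAE window. The natural reading of the deaths row is all deaths, and the choice of first or last dose moves the cut by at most 2 days.

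Much of this is fair and limits the point. The deaths row and the dose anchor are minor, and 83% is a share of days, not of events. Three things still stand. The rationale does not explain why worsenings keep the full follow-up. A listing is not an incidence table, and no planned summary covers new non-serious events after about day 30 although the objective runs to day 180. An openly stated rule that departs from the protocol still belongs in Section 5.

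The follow-up period has no separate definition in the protocol; day 180 is inferred from the visit schedule and the safety objective, which agree. The SAP also cites several country versions of the protocol. SAP Section 1 says that these differ only in inclusion criteria, so it offers no version difference that would explain the change.

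**Conclusion.** The concern holds. SAP 4.5.1 shortens the treatment-emergent window for new AEs from about 180 days to 30, keeps the longer window for worsenings, and does not declare the departure. Outside the new window lie 150 of 180 days (83%; 81% to 85% allowing for the visit window and a second dose) and 4 of 11 AE visits. All 4 TEAE summary tables and 4 of 5 overview rows are affected; the scope of the 2 SAE tables is ambiguous, and so, less seriously, is that of the deaths row.

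The share of events that would go untabulated cannot be derived from the documents. The patterns tried give 23% to 83%, and these rest wholly on assumed onset rates. The fault lies in definition and presentation and can be corrected without new data. It should be put right because AE incidence to day 180 is part of the stated safety objective.

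**What to change.** In SAP 4.5.1:

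- Define a TEAE for the summary tables as any AE that starts or worsens after the first dose, through the day 180 visit. Protocol 6.3.3 also has an exception for pre-dose events that are procedure-related or serious; say how these are handled, so that the revision does not bring in another unstated difference.
- Keep the residual-effect view as a split by onset, to day 30 and after day 30, in the total column only. With 3 patients in the two-dose group, a further split there would add little.
- State that SAEs and deaths are tabulated through day 180.
- State whether the 30 days run from the first or the last dose.

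In SAP Section 5, declare any departure from the protocol definition that is kept, with its reason.

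The cost is SAP wording, one onset flag in the AE analysis data set, and onset columns in the overview and AE summary tables. The events are already collected through follow-up. The drawback is higher TEAE counts that include events due to transplantation or co-medication; the onset split makes the late ones visible.

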#### **Summary tables will be prepared for:**

- All TEAEs
- TEAEs by causality (related/unrelated)
- TEAEs by intensity
- Related TEAEs by intensity
- SAEs
- SAEs by causality (related/unrelated)

#### **Data listings will be provided for:**

- All TEAEs sorted by patient number and start time
- All TEAEs sorted by MedDRA SOC and PT

- SAEs
- SAEs leading to death
- TEAEs leading to discontinuation of study drug
- TEAEs leading to withdrawal
- Pre-treatment AEs
- Post-treatment AEs

#### **4.5.2 Other safety endpoints**

Clinical laboratory tests will be summary tabulated and presented graphically as box plots.

The immunogenicity profile of imlifidase is evaluated by measuring ADA, which will be be summary tabulated and presented graphically as box plots.

Vital signs will be summary tabulated.

ECG will be listed.

The kidney function after imlifidase treatment is assessed by kidney biopsies on day 180, filtration rate (eGFR), plasma creatinine and proteinuria up to 180 days post treatment. These variables are all presented together with the safety laboratory tests. Each variable will be tabulated by time point

The eGFR will be calculated as described in the MDRD equation [1]:

$$\text{eGFR (mL/min/1.73 m}^2\text{)} = 175 \times (\text{sCr})^{-1.154} \times (\text{Age})^{-0.203} \times (0.742 \text{ if female}) \times (1.212 \text{ if African American}),$$

where sCr stands for creatinine value in serum.

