4.1 Overall study design and flowcharts

This is a phase II, open label exploratory study to assess the IdeS efficacy in creating a negative crossmatch test (CXM) in a total of 15-20 patients (7-13 with living donors and 7-13 with a deceased donor) who exhibit DSAs and have a positive crossmatch test to their available live or deceased donors. The first 3 patients in this study will receive a kidney from a deceased donor. The study will primarily examine the efficacy of IdeS in creating a negative CXM in these patients. Included patients will be treated with IdeS on day 0. If it is considered safe and the desired effect is not achieved (negative crossmatch) a second dose can be given within 2 days of the first infusion. In addition to IdeS patients

will be given high dose IVIg (2 g/kg BW, maximum of 140 g) on day 7 and anti CD20 (Rituximab) on day 9 as outlined in [Figure 1](#). DSA levels will be monitored 2, 6, 24 and 48 hours and 7, 14, 21, 28, 64, 90, 120 and 180 days after the last IdeS dosing. Safety, including kidney function will be monitored at multiple time points up to 180 days after treatment. Pharmacokinetics, pharmacodynamics and anti-drug antibodies will be followed. For details on assessments see flow chart in [Table 1](#). Patients who are not eligible for transplantation after IdeS treatment will not be transplanted and thus will not receive any induction therapy or immunosuppression. All patients who receive IdeS will also be asked to remain in the study and be followed up according to the study protocol even if they are not transplanted. In addition, patients who lose their graft during the course of the study will remain in the study and be followed up according to the study protocol.

[figure not shown]

Figure 1. Overall treatment schedule. CXM=crossmatch test, Tx=transplantation.

Table 1. Study flow chart: Screening to Day 180 after IdeS infusion

Study visit	1	2	3	4	5	6	7	8	9	10	11	12
Day	Screening -28-0	0-2	3-6	7	9	14	21	28	64	90	120	180
Assessment /Time window				+/- 1 d	+ 2 d	+/- 2 d	+/- 3 d	+/- 3 d	+/-7 d	+/-7 d	+/-14 d	+/-14 d
Informed Consent	X											
Demographics and medical/surgical history	X	X										
Inclusion/exclusion	X	X										
Physical examination	X											X
Weight	X	X				X						
Height	X											
Vital signs	X	X		X ^c				X		X	X	X
Body temperature	X	X										
CDC and FACS	X	X ^a										
DSAs	X	X		X ^c		X	X	X	X	X	X	X
Pregnancy test (serum)	X	X ^b										X
Adverse events		X	X	X	X	X	X	X	X	X	X	X

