## 2 Study design

This is a phase II, open label exploratory study to assess the imlifidase efficacy in creating a negative crossmatch test (CXM) in a total of 15-20 patients (7-13 with living donors and 7-13 with a deceased donor) who exhibit DSAs and have a positive crossmatch test to their available live donors. The first 3 patients in this study will receive a kidney from a deceased donor. The study will primarily examine the efficacy of imlifidase in creating a negative CXM in patients. Included patients will be treated with imlifidase on day 0. If it is considered safe and the desired effect is not achieved (negative crossmatch) a second dose can be given within 2 days of the first infusion. In addition to imlifidase patients will be given high dose IVIg (2 g/kg BW, maximum of 140 g) on day 7 and anti CD20 (Rituximab) on day 9 as outlined in [Figure 1](#). DSA levels will be monitored 2, 6, 24 and 48 hours and 7, 14, 21, 28, 64, 90, 120 and 180 days after the last imlifidase dosing. Safety, including kidney function will be monitored at multiple time points up to 180 days after treatment. PK, PD and ADA will be followed. For details on assessments see flow chart in [Table 1](#). Patients who are not eligible for transplantation after imlifidase treatment will not be transplanted and thus will not receive any induction therapy or immunosuppression. All patients who receive imlifidase will also be asked to remain in the study and be followed up according to the study protocol even if they are not transplanted. In addition, patients who lose their graft during the course of the study will remain in the study and be followed up according to the study protocol and clinical practice at the respective site.

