### 4.3 Demographics and other baseline characteristics

The following demographic and body measurements variables will be summarised: age, sex, race, height, weight and BMI.

Medical and surgical history and concomitant illness will be summarised by MedDRA system organ class (SOC) and preferred term (PT) version 18.1. Prior and concomitant medication will be tabulated by WHO drug version 153E, level 4 (chemical/therapeutic/pharmacological subgroup) and level 5 (Chemical substance). Medication is categorised as “Started prior to study start” and “Ongoing” in the eCRF and these responses will be used to categorise as prior and concomitant respectively. Medication was recorded in the original eCRF. The additional data recording collected specifically medication for de-sensitization and rejection. There may therefore be an overlap with prior and concomitant medication and the de-sensitization and rejection medication will be tabulated separately.

Previous kidney transplant history will be summary tabulated.

Baseline assessments of ECG, physical examination, vital signs, body measurements and laboratory parameters will be presented as part of the general tables and listings for these parameters.

ImmunoCAP IgE (ADA) is recorded at baseline only and will be listed. Serology and sperm sample will be listed.

The drug exposure will be listed showing number of doses, planned dose and actual dose per kg BW.

Donor characteristics will be listed.

Recipient and donor HLA types will be listed.

Recipient and donor blood groups will be listed.

Deceased donor characteristics will be listed.

Protocol deviations will be listed.

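### The kidney-function tables pool all dosed patients and apply MDRD to every creatinine value, so if anyone lacks a working graft the means and SDs cannot describe graft function

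*SAP*

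**What the plan says.** SAP 1.1.2 names kidney function (eGFR, creatinine and proteinuria, to day 180) as a secondary endpoint. SAP 4.5.2 places it with the safety data: "These variables are all presented together with the safety laboratory tests. Each variable will be tabulated by time point". On derivation it says: "The eGFR will be calculated as described in the MDRD equation". No exception is given for creatinine measured on dialysis.

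SAP 4.5 evaluates safety on the safety analysis set, which SAP 3.1 defines as everyone given any study drug; transplantation is not required. The only grouping is in SAP 4.1: "Efficacy and safety tabulations will be by number of administrations (1 or 2 doses) and total including all patients".

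Both documents keep patients without a working graft under observation. Under Protocol 4.1, dosed patients will "be asked to remain in the study and be followed up according to the study protocol even if they are not transplanted", and "patients who lose their graft during the course of the study will remain in the study". SAP 2 repeats this: "All patients who receive imlifidase will also be asked to remain in the study".

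SAP 1 reports that amendment 7 added a CRF that covers transplantation outcome. SAP 4.3 uses other parts of that collection ("The additional data recording collected specifically medication for de-sensitization and rejection"), but 4.5.2 does not mention transplantation outcome. SAP 4.1 also states: "All data will be listed".

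**The concern.** In a transplanted patient with a working graft, creatinine and MDRD eGFR measure how the graft filters. In a patient on dialysis, creatinine mainly reflects the dialysis schedule, and the MDRD value computed from it has no useful meaning. The plan puts both kinds of value into the same mean and SD at each time point. The split by number of doses does not separate them, because it is unrelated to graft status.

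The trial tests no hypothesis, so the descriptive tables are the result. A reader will naturally take the day-180 row as the function of the grafts. If one or more patients in that row have no graft, the mean and SD describe neither those with a graft nor those without, and nothing in the SAP says the table will show how many of each it contains.

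**Working it through.** **Text check.** Four questions were put to the two documents.

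1. Can a dosed patient be without a working graft and still have kidney function measured? Yes: Protocol 4.1 and SAP 2, quoted above.
2. Is that patient in the kidney-function table? Yes: SAP 3.1, 4.5 and 4.1 include everyone dosed.
3. Is there a split or restriction by graft status? None is stated.
4. Is there a rule for values taken on dialysis? None. The protocol mentions dialysis in background text, in the AE/SAE definitions (6.3.2) and in SUSAR reporting (6.3.9). The SAP text does not mention it. SAP 4.1 says only that missing data are in general not imputed.

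The plan states no figure on this point, so there is none to reproduce.

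**Illustration of size.** The SAP formula is 175 × sCr^−1.154 × age^−0.203, with factors 0.742 (female) and 1.212 (African American).

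Assumptions, none of them from the documents:
- sCr in mg/dL, man aged 45, factor 1.212 not applied
- creatinine 1.4 with a working graft, the same in every such patient, at a later visit when graft function has settled
- creatinine 8 on dialysis

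Results per patient:
- sCr 1.4 gives eGFR 54.8
- sCr 8 gives eGFR 7.3
- gap 54.8 − 7.3 = 47.5

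With k patients without a graft among n, the mean falls by k × 47.5 / n. The planned total is 15 to 20 patients.

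| Total column | n = 20 | n = 15 |
|---|---|---|
| Fall in mean eGFR, k = 1 | 47.5/20 = 2.4 (54.8 to 52.4) | 47.5/15 = 3.2 (54.8 to 51.6) |
| Fall in mean eGFR, k = 2 | 95/20 = 4.7* | 95/15 = 6.3 |
| SD of eGFR, k = 1 (gap/√n) | 10.6 | 12.3 |
| Mean creatinine, k = 1 | (19 × 1.4 + 8)/20 = 1.73 | (14 × 1.4 + 8)/15 = 1.84 |

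*From the unrounded gap.

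The SD would be 0 without the extra patient, because all grafts were set equal. The median stays at 54.8 in these cases.

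**Range for one patient.** Let graft creatinine run from 1.2 to 1.8 and dialysis creatinine from 5 to 10 mg/dL.
- Smallest gap: 41.0 − 12.6 = 28.4. The fall is 1.4 (n=20) or 1.9 (n=15).
- Largest gap: 65.5 − 5.7 = 59.8. The fall is 3.0 (n=20) or 4.0 (n=15).

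No figure is offered for proteinuria, because the documents give no basis for one.

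**The case against.** The strongest reply is that the endpoint is kidney function after treatment, reported as safety in everyone dosed. Including patients for whom treatment did not lead to a working graft is then a legitimate choice. This stands: the all-treated table is not an error and should not be replaced. It does not answer what the grafts do, and no planned table does.

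Second, the presentation already limits the harm. SAP 4.1 plans median, minimum and maximum, 4.5.2 plans box plots for laboratory tests, and all data are listed by patient. Biopsies on day 180 are part of the kidney-function assessment, and the DSMB watches graft losses. With 15 to 20 patients, a careful reader could match outlying creatinine values to outcomes by hand. This lowers the weight but does not close the gap, because the SAP does not say that any of these displays marks graft status. The table shells are separate documents that were not available, so a split there cannot be ruled out. SAP 8 lets the templates change after signature, so it would not be a commitment in the SAP.

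Third, the documents do not show that any patient lacked a graft. This stands in full, and the size is conditional on it.

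A reader might also infer that eGFR on dialysis should not be calculated at all. That would do damage: with no imputation, dropping those values would silently remove the worst patients from the all-treated table.

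**Conclusion.** The point holds as an inexpensive improvement in presentation, at modest weight. Followed as written, the plan can produce means and SDs of a named secondary endpoint that mix graft function with dialysis creatinine. Such a table cannot describe graft function.

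The size is illustrative only. Under the assumptions above, one patient without a graft lowers the total mean eGFR by about 2.4 to 3.2 (1.4 to 4.0 over the wider creatinine range), and none gives zero.

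Two stronger readings are not supported. One is that the trial's kidney-function results are in fact distorted: the documents give no count of never-transplanted, graft-loss or dialysed patients. The other is that the two-dose column is badly affected. One such patient among its 3 would lower the mean by 47.5/3 = 15.8, but nothing places such a patient there.

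**What to change.** In SAP 4.5.2:

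- Keep the all-treated table as planned, with no values deleted.
- Add a supplementary summary of eGFR, creatinine and proteinuria in patients with a functioning graft at each visit, derived from the transplantation-outcome CRF. Show the total column only, since means in a two-dose group of 3 say little.
- Beside it, give at each time point the number treated, transplanted, with a functioning graft, with a lost graft, and on dialysis. Count temporary dialysis separately from graft loss.
- Flag values taken on dialysis in the listing, and footnote that MDRD eGFR is not interpretable there. Do not suppress it.

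The cost is a derived status variable, one extra table per variable and a footnote. Transplantation outcome is already collected, but the CRF itself is not shown. Status by visit and dialysis dates may therefore need checking against it.

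The downside is that the functioning-graft rows condition on something that happens after treatment, so they will look favourable. They should only supplement the all-treated table and never appear without the counts.
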